Table 10.1	
Vessel Transection Summary – Original Procedure ENSEAL Analysis Set
 
Subjects With Medical History for Treatment of Cancer
 
Programming note: Subgroup of subjects who had medical history of treatment for cancer is identified from “Treatment History Form” for patients who checked the “neoadjuvant chemotherapy” or “neoadjuvant radiation”.

------------	--

«CRF_2_0_PROD_16DEC21_RP: _aCRF - Unique
Form: Treatment History
Generated On: 08 Jun 2022 10:48:09

Type of treatment within 90 days prior to surgery (check all that apply):

None ②

Observation ③

Neoadjuvant chemotherapy ④

If the subject is taking neoadjuvant chemotherapy specify:

Treatment regimen: ⑤

Start date: Fixed Unit: DD/MMM/YYYY ⑥

Stop date: Fixed Unit: DD/MMM/YYYY ⑦

Neoadjuvant radiation therapy ⑧

If the subject is taking neoadjuvant radiation therapy specify:

Anatomic location: ⑨

Start date: ⑩

Stop date: ⑪

Surgery ⑫

Pre-operative Stage (using TNM staging system): ⑬

If pre-operative stage is not present, specify reason: Not applicable ⑭

Unknown ⑮

Definitive Stage (using TNM staging system): ⑯

If definitive stage is not present, specify reason: Not applicable ⑰

Unknown ⑱

The following tables will have the same format as Table 9:

Table 10.2	
Vessel Transection Summary – Original Procedure ENSEAL Analysis Set
 
Subjects Without Medical History for Treatment of Cancer
 
Programming note: Subgroup of subjects who had medical history of treatment for cancer is identified from “Treatment History Form” for patients who checked the “neoadjuvant chemotherapy” or “neoadjuvant radiation”.
 
Subjects without Medical History for Treatment of Cancer is identified who did not change any of the boxes from “Treatment History Form” of the questions “neoadjuvant chemotherapy” and “neoadjuvant radiation”.

------------	--

Bookmarks

- Annotations
- Background Information Thoracic
- Annotations
- Background Information Urologic
- Annotations
- Treatment History Summary
- Annotations
- Treatment History**
- Annotations
- Device Log
- Annotations
- Intra-Operative Data

eCRF_2_0_PROD_16DEC21_RP: _aCRF - Unique
Form: Treatment History
Generated On: 08 Jun 2022 10:48:09

Type of treatment within 90 days prior to surgery (check all that apply):

None ②

Observation ③

Neoadjuvant chemotherapy ④

If the subject is taking neoadjuvant chemotherapy specify:

Treatment regimen: _____

Start date: _____ Fixed Unit: DD/MMM/YYYY ⑥

Stop date: _____ Fixed Unit: DD/MMM/YYYY ⑧

Neoadjuvant radiation therapy ⑨

If the subject is taking neoadjuvant radiation therapy specify:

Anatomic location: _____ ⑪

Start date: _____ ⑫

Stop date: _____ ⑬

Surgery: _____ ⑭

Pre-operative Stage (using TNM staging system): _____

If pre-operative stage is not present, specify reason: _____

Not applicable ⑯

Unknown ⑯

Definitive Stage (using TNM staging system): _____

If definitive stage is not present, specify reason: _____

Not applicable ⑰

Unknown ⑰

Table 11
 Surgeon Questionnaire – ENSEAL X1
 ENSEAL Analysis Set

Characteristic	Thoracic n (%)	Urologic n (%)	ENT n (%)	Total n (%)
Number of Questionnaires Completed	xx	xx	xx	xx
What advanced bipolar device(s) did you previously use (check all that apply) ¹				
None	xx (xx.x)	xx (xx.x)	xx (xx.x)	xx (xx.x)
ENSEAL® Trio Tissue Sealers	xx (xx.x)	xx (xx.x)	xx (xx.x)	xx (xx.x)
ENSEAL® Round Tip Tissue Sealer	xx (xx.x)	xx (xx.x)	xx (xx.x)	xx (xx.x)
ENSEAL® G2 Curved and Straight Tissue Sealer	xx (xx.x)	xx (xx.x)	xx (xx.x)	xx (xx.x)
ENSEAL® G2 Articulating Tissue Sealer	xx (xx.x)	xx (xx.x)	xx (xx.x)	xx (xx.x)
Ligasure Maryland	xx (xx.x)	xx (xx.x)	xx (xx.x)	xx (xx.x)
Ligasure Blunt Tip	xx (xx.x)	xx (xx.x)	xx (xx.x)	xx (xx.x)
Thunderbeat	xx (xx.x)	xx (xx.x)	xx (xx.x)	xx (xx.x)
Other	xx (xx.x)	xx (xx.x)	xx (xx.x)	xx (xx.x)
I experienced less hand fatigue using the ENSEAL® X1 device compared to previous advanced bipolar device use				
Strongly disagree	xx (xx.x)	xx (xx.x)	xx (xx.x)	xx (xx.x)
Slightly disagree	xx (xx.x)	xx (xx.x)	xx (xx.x)	xx (xx.x)
Neutral	xx (xx.x)	xx (xx.x)	xx (xx.x)	xx (xx.x)
Slightly agree	xx (xx.x)	xx (xx.x)	xx (xx.x)	xx (xx.x)
Strongly agree	xx (xx.x)	xx (xx.x)	xx (xx.x)	xx (xx.x)
The cut and seal buttons were easily distinguishable on the ENSEAL® X1 device				
Strongly disagree	xx (xx.x)	xx (xx.x)	xx (xx.x)	xx (xx.x)
Slightly disagree	xx (xx.x)	xx (xx.x)	xx (xx.x)	xx (xx.x)
Neutral	xx (xx.x)	xx (xx.x)	xx (xx.x)	xx (xx.x)
Slightly agree	xx (xx.x)	xx (xx.x)	xx (xx.x)	xx (xx.x)
Strongly agree	xx (xx.x)	xx (xx.x)	xx (xx.x)	xx (xx.x)
The ENSEAL® X1 device reduced the need for instrument exchanges during surgery compared to previous advanced bipolar device use				
Strongly disagree	xx (xx.x)	xx (xx.x)	xx (xx.x)	xx (xx.x)
Slightly disagree	xx (xx.x)	xx (xx.x)	xx (xx.x)	xx (xx.x)
Neutral	xx (xx.x)	xx (xx.x)	xx (xx.x)	xx (xx.x)
Slightly agree	xx (xx.x)	xx (xx.x)	xx (xx.x)	xx (xx.x)
Strongly agree	xx (xx.x)	xx (xx.x)	xx (xx.x)	xx (xx.x)

The ENSEAL® X1 device was easier to use compared to previous advanced bipolar device use

Strongly disagree	xx (xx.x)	xx (xx.x)	xx (xx.x)	xx (xx.x)
Slightly disagree	xx (xx.x)	xx (xx.x)	xx (xx.x)	xx (xx.x)
Neutral	xx (xx.x)	xx (xx.x)	xx (xx.x)	xx (xx.x)
Slightly agree	xx (xx.x)	xx (xx.x)	xx (xx.x)	xx (xx.x)
Strongly agree	xx (xx.x)	xx (xx.x)	xx (xx.x)	xx (xx.x)

Overall, on the most critical tasks in the cases, the ENSEAL® X1 device performed better than my previous advanced bipolar device

Strongly disagree	xx (xx.x)	xx (xx.x)	xx (xx.x)	xx (xx.x)
Slightly disagree	xx (xx.x)	xx (xx.x)	xx (xx.x)	xx (xx.x)
Neutral	xx (xx.x)	xx (xx.x)	xx (xx.x)	xx (xx.x)
Slightly agree	xx (xx.x)	xx (xx.x)	xx (xx.x)	xx (xx.x)
Strongly agree	xx (xx.x)	xx (xx.x)	xx (xx.x)	xx (xx.x)

Percentages are calculated using the total number of questionnaires completed in each group as the denominator.

1 Multiple response are collected.

Table 12
 Surgeon Questionnaire – Generator
 ENSEAL Analysis Set

Characteristic	Thoracic n (%)	Urologic n (%)	ENT n (%)	Total n (%)
Software version used in the generator				
2013-1	xx (xx.x)	xx (xx.x)	xx (xx.x)	xx (xx.x)
2014-1	xx (xx.x)	xx (xx.x)	xx (xx.x)	xx (xx.x)
2016-1	xx (xx.x)	xx (xx.x)	xx (xx.x)	xx (xx.x)
2016-1.1	xx (xx.x)	xx (xx.x)	xx (xx.x)	xx (xx.x)
Other	xx (xx.x)	xx (xx.x)	xx (xx.x)	xx (xx.x)
What instrument was used with the generator?				
Study device (ENSEAL X1 Curved Jaw)	xx (xx.x)	xx (xx.x)	xx (xx.x)	xx (xx.x)
HARMONIC instrument	xx (xx.x)	xx (xx.x)	xx (xx.x)	xx (xx.x)
Other ENSEAL instrument	xx (xx.x)	xx (xx.x)	xx (xx.x)	xx (xx.x)
Were there any specific generator-related alarms generated?				
Yes	xx (xx.x)	xx (xx.x)	xx (xx.x)	xx (xx.x)
No	xx (xx.x)	xx (xx.x)	xx (xx.x)	xx (xx.x)
Type of generator-related alarms generated (select all that apply)				
Reactivate	xx (xx.x)	xx (xx.x)	xx (xx.x)	xx (xx.x)
Restart generator	xx (xx.x)	xx (xx.x)	xx (xx.x)	xx (xx.x)
Press OK to continue	xx (xx.x)	xx (xx.x)	xx (xx.x)	xx (xx.x)

Please contact your sales representative	xx (xx.x)	xx (xx.x)	xx (xx.x)	xx (xx.x)
Generator overheating	xx (xx.x)	xx (xx.x)	xx (xx.x)	xx (xx.x)
Software upgrade required to run instrument	xx (xx.x)	xx (xx.x)	xx (xx.x)	xx (xx.x)
Other	xx (xx.x)	xx (xx.x)	xx (xx.x)	xx (xx.x)
 The generator performed as intended				
Strongly disagree	xx (xx.x)	xx (xx.x)	xx (xx.x)	xx (xx.x)
Slightly disagree	xx (xx.x)	xx (xx.x)	xx (xx.x)	xx (xx.x)
Neutral	xx (xx.x)	xx (xx.x)	xx (xx.x)	xx (xx.x)
Slightly agree	xx (xx.x)	xx (xx.x)	xx (xx.x)	xx (xx.x)
Strongly agree	xx (xx.x)	xx (xx.x)	xx (xx.x)	xx (xx.x)
 The touchscreen allowed for easy set-up and operation				
Strongly disagree	xx (xx.x)	xx (xx.x)	xx (xx.x)	xx (xx.x)
Slightly disagree	xx (xx.x)	xx (xx.x)	xx (xx.x)	xx (xx.x)
Neutral	xx (xx.x)	xx (xx.x)	xx (xx.x)	xx (xx.x)
Slightly agree	xx (xx.x)	xx (xx.x)	xx (xx.x)	xx (xx.x)
Strongly agree	xx (xx.x)	xx (xx.x)	xx (xx.x)	xx (xx.x)

Percentages are calculated using the total number of questionnaires completed in each group as the denominator.

Programming note: If fewer than 10 surveys are completed in total, results will only be listed.

Table 13
 Blood Transfusion Summary
 ENSEAL Analysis Set

Characteristic	Thoracic (n = xx)	Urologic (n = xx)	ENT (n = xx)	Total (n = xx)
Blood Transfusion Required?, n (%)				
Yes	xx (xx.x)	xx (xx.x)	xx (xx.x)	xx (xx.x)
No	xx (xx.x)	xx (xx.x)	xx (xx.x)	xx (xx.x)
Total required units of blood				
N	xx	xx	xx	xx
Mean (SD)	xx.x (xx.x)	xx.x (xx.x)	xx.x (xx.x)	xx.x (xx.x)
Median (Min, Max)	xx.x (xx, xx)	xx.x (xx, xx)	xx.x (xx, xx)	xx.x (xx, xx)
Time Point of Transfusion, n (%)				
Intra-operatively	xx (xx.x)	xx (xx.x)	xx (xx.x)	xx (xx.x)
Prior to discharge	xx (xx.x)	xx (xx.x)	xx (xx.x)	xx (xx.x)
After discharge	xx (xx.x)	xx (xx.x)	xx (xx.x)	xx (xx.x)

Percentages for time point of transfusion are calculated using the number of subjects requiring a blood transfusion as the denominator.

Table 14
 All Adverse Events by System Organ Class and Preferred Term
 ENSEAL Analysis Set

System Organ Class	Preferred Term	Thoracic		Urologic		ENT		Total	
		Subject n (%)	Events						
Total Number of AE			xx		xx		xx		xx
Number of Subjects With at Least 1 AE		xx (xx.x)		xx (xx.x)		xx (xx.x)		xx (xx.x)	
System Organ Class 1	Total	xx (xx.x)	xx						
	Preferred Term 1	xx (xx.x)	xx						
	Preferred Term 2	xx (xx.x)	xx						
	Preferred Term 3	xx (xx.x)	xx						
System Organ Class 2	Total	xx (xx.x)	xx						
	Preferred Term 1	xx (xx.x)	xx						
	Preferred Term 2	xx (xx.x)	xx						
System Organ Class 3	Total	xx (xx.x)	xx						
	Preferred Term 1	xx (xx.x)	xx						
	Preferred Term 2	xx (xx.x)	xx						
	Preferred Term 3	xx (xx.x)	xx						
System Organ Class 4	Total	xx (xx.x)	xx						
	Preferred Term 1	xx (xx.x)	xx						
	Preferred Term 2	xx (xx.x)	xx						

If a subject has multiple occurrences of an AE, it is counted only once in the respective subject column for the corresponding AE. Percentages are calculated as $(n/N)*100$ where N represents total number of subjects in the column header.

If a subject has multiple occurrences of an AE, all events are counted in the respective event column for the corresponding AE.

The following tables will have the same format as Table 14:

Table 15	All Serious Adverse Events by System Organ Class and Preferred Term ENSEAL Analysis Set
Table 16	Adverse Events Related to the Study Device by System Organ Class and Preferred Term ENSEAL Analysis Set Footnote: Related AEs include those having a relationship of possibly, probably, or causally
Table 17	Serious Adverse Events Related to the Study Device by System Organ Class and Preferred Term ENSEAL Analysis Set Footnote: Related AEs include those having a relationship of possibly, probably, or causally
Table 18	Adverse Events Related to the Study Procedure by System Organ Class and Preferred Term ENSEAL Analysis Set Footnote: Related AEs include those having a relationship of possibly, probably, or causally
Table 19	Serious Adverse Events Related to the Study Procedure by System Organ Class and Preferred Term ENSEAL Analysis Set Footnote: Related AEs include those having a relationship of possibly, probably, or causally

Table 21
 Protocol Deviations
 ENSEAL Analysis Set

Characteristic	Thoracic n (%)	Urologic n (%)	ENT n (%)	Total n (%)
Total Number of Protocol Deviations	xxx	xxx	xxx	xxx
Specific Types of Protocol Deviations ¹				
AE/SAE Reporting	xx (xx.x)	xx (xx.x)	xx (xx.x)	xx (xx.x)
Assessment Related	xx (xx.x)	xx (xx.x)	xx (xx.x)	xx (xx.x)
Consent Related	xx (xx.x)	xx (xx.x)	xx (xx.x)	xx (xx.x)
Inclusion/Exclusion Criteria	xx (xx.x)	xx (xx.x)	xx (xx.x)	xx (xx.x)
Procedure Related	xx (xx.x)	xx (xx.x)	xx (xx.x)	xx (xx.x)
Visit Related	xx (xx.x)	xx (xx.x)	xx (xx.x)	xx (xx.x)
Other	xx (xx.x)	xx (xx.x)	xx (xx.x)	xx (xx.x)
Did this deviation result in the subject's discontinuation of study?				
Yes	xx (xx.x)	xx (xx.x)	xx (xx.x)	xx (xx.x)
No	xx (xx.x)	xx (xx.x)	xx (xx.x)	xx (xx.x)
Primary rationale for deviation				
To protect the subject's rights, safety, or well-being	xx (xx.x)	xx (xx.x)	xx (xx.x)	xx (xx.x)
Site staff error	xx (xx.x)	xx (xx.x)	xx (xx.x)	xx (xx.x)
Subject physically unable to have / complete test	xx (xx.x)	xx (xx.x)	xx (xx.x)	xx (xx.x)
Due to subject / physician unavailability	xx (xx.x)	xx (xx.x)	xx (xx.x)	xx (xx.x)
Subject refused	xx (xx.x)	xx (xx.x)	xx (xx.x)	xx (xx.x)
Other	xx (xx.x)	xx (xx.x)	xx (xx.x)	xx (xx.x)
Sponsor Assessment of Protocol Deviations ¹				
Minor	xx (xx.x)	xx (xx.x)	xx (xx.x)	xx (xx.x)
Major	xx (xx.x)	xx (xx.x)	xx (xx.x)	xx (xx.x)
Number (%) of Subjects With at Least 1 Protocol Deviation ²	xx (xx.x)	xx (xx.x)	xx (xx.x)	xx (xx.x)

1 Denominator used is the total number of protocol deviations reported.

2 Denominator used is the total number of subjects in the column header.

ETHICON, Inc.
Protocol Number: ENG-2020-04
Page x of y

Program Name: XXXXXXXX.sas
Run Date: mm/dd/yyyy hh:mm
Data Last Modified: mm/dd/yyyy hh:mm

The following listings will be generated for this study:

Listing 1	Inclusion/Exclusion Criteria All Subjects
Listing 2	Demographics All Subjects
Listing 3	Vital Signs All Subjects
Listing 4	Medical History All Subjects
Listing 5	Surgical History All Subjects
Listing 6	Background Information All Subjects
Listing 7.1	Background Information ENT All Subjects
Listing 7.2	Background Information Thoracic All Subjects
Listing 7.3	Background Information Urologic All Subjects
Listing 8	Treatment History All subjects
Listing 9	Intra-Operative Data All Subjects
Listing 10	ENSEAL X1 Usage All Subjects
Listing 11	Vessel Transected All Subjects
Listing 12	Prophylactic Clip/Suture Use All Subjects
Listing 13	Grade 3 Form

	All Subjects
Listing 14	Grade 4 Form All Subjects
Listing 15	Device Log All Subjects
Listing 16	X1 Curved Jaw Surgeon Questionnaire All Subjects
Listing 17	Generator Questionnaire All Subjects
Listing 18	Blood Transfusion Detail All Subjects
Listing 19	Discharge All Subjects
Listing 20	Subject Completion/Discontinuation All Subjects
Listing 21	Protocol Deviations All Subjects
Listing 22	Concomitant Procedures All Subjects
Listing 23	Prior Concomitant Medications All Subjects
Listing 24	Adverse Events All Subjects
Listing 25	Study Visits All Subjects

Signature Page for VTMF-17865130, V-TMF Version: 1.0
ENG_2020_04---Statistical Analysis Plan-28 Sep 2022

Approved - 28-Sep-2022 14:25:03 GMT+0000	[name], Biostatistics
Approved - 28-Sep-2022 15:57:46 GMT+0000	[name], XS - Clinical Science
Approved - 29-Sep-2022 12:55:09 GMT+0000	[name], Biostatistics

Signature Meaning:

To verify that the content is accurate and true to the best of my knowledge.

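### SAP Table 11 divides four comparative surgeon items by all completed questionnaires, so any surgeon with no previous advanced bipolar device counts in a comparison they cannot make

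*SAP*

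**What the plan says.** The SAP Appendix, Table 11, opens with the question "What advanced bipolar device(s) did you previously use (check all that apply", and the first response row is *None*. Five agreement items follow, each with five categories from strong disagreement to strong agreement and no row for not applicable. Four of the five are comparative:

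- Hand fatigue: "I experienced less hand fatigue using the ENSEAL® X1 device compared to previous advanced bipolar device use"
- Instrument exchanges: "The ENSEAL® X1 device reduced the need for instrument exchanges during surgery compared to previous advanced bipolar device use"
- Ease of use: "The ENSEAL® X1 device was easier to use compared to previous advanced bipolar device use"
- Critical tasks: "Overall, on the most critical tasks in the cases, the ENSEAL® X1 device performed better than my previous advanced bipolar device"

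The fifth concerns ENSEAL X1 alone: "The cut and seal buttons were easily distinguishable on the ENSEAL® X1 device".

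The footnote on percentages is "Percentages are calculated using the total number of questionnaires completed in each group as the denominator". It makes no exception by item. No other footnote, programming note or SAP section says how surgeons who answered *None* are handled on the comparative items.

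**The concern.** The shell provides for surgeons with no comparator and then keeps them in the denominator of items that need one. A reader of the report will take a statement that ENSEAL X1 outperformed the surgeon's previous device as coming from surgeons who had such a device. Under the footnote that need not be so.

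The questionnaire is completed once per investigator (SAP 8.4.3), so the numbers are likely to be small, and Table 11 splits them further into three procedure columns. One or two *None* answers could therefore shift a printed percentage visibly. At stake is how the surgeon-preference results are read, not any primary, secondary or safety result.

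**Working it through.** **What the plan gives.** It states no figure on this point, so there is nothing to reproduce. Protocol 3.2.1 allows up to 12 centres. Neither document gives the number of investigators or the expected share without a previous device. All counts below are therefore assumptions.

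**Notation.** N = questionnaires completed; k = those answering *None*; a = surgeons with a previous device who agree with the item; x = *None* surgeons who answer and agree (0 to k). Surgeons with a previous device are assumed to answer every item.

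**Formulas.**
- Among surgeons able to compare: a/(N − k).
- Under the footnote, *None* surgeons leave the item blank: a/N. The five categories then sum to (N − k)/N instead of 100%, and each is understated by that factor.
- Under the footnote, *None* surgeons answer: (a + x)/N. This exceeds a/(N − k) only when x/k exceeds a/(N − k).

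**Blank answers.**
- N = 12, k = 3, a = 6: printed 6/12 = 50.0%; among those able to compare 6/9 = 66.7%.
- N = 12, k = 2, a = 7: printed 7/12 = 58.3%; among those able to compare 7/10 = 70.0%.
- With N = 12, the categories sum to 11/12 = 91.7% for k = 1, 9/12 = 75.0% for k = 3, and 6/12 = 50.0% for k = 6.

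**Full range, from x = 0 (also the blank case) to x = k.**

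| N | k | a | Printed, lowest | Printed, highest | Able to compare |
|---|---|---|---|---|---|
| 12 | 0 | 9 | 9/12 = 75.0% | 9/12 = 75.0% | 9/12 = 75.0% |
| 12 | 1 | 8 | 8/12 = 66.7% | 9/12 = 75.0% | 8/11 = 72.7% |
| 12 | 3 | 7 | 7/12 = 58.3% | 10/12 = 83.3% | 7/9 = 77.8% |
| 12 | 6 | 4 | 4/12 = 33.3% | 10/12 = 83.3% | 4/6 = 66.7% |
| 24 | 3 | 16 | 16/24 = 66.7% | 19/24 = 79.2% | 16/21 = 76.2% |
| 4 (one procedure column) | 1 | 2 | 2/4 = 50.0% | 3/4 = 75.0% | 2/3 = 66.7% |

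The first row shows that the two denominators agree when nobody answers *None* and nothing is blank.

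**Comparison with other shells.** Elsewhere the SAP restricts the denominator of conditional items. Table 8 bases satisfaction scores on cases where the device was used for that task. Table 9 bases the Grade 3 and Grade 4 details on vessels of that grade. Table 13 bases transfusion timing on subjects transfused. Table 2 uses non-missing data, and females only for childbearing potential. Table 11 departs from that practice. SAP 8.7 also says summaries use observed data, which sits badly with a denominator that counts blank answers.

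**The case against.** Several points on the other side have force.

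- **The problem is conditional.** A reader might infer that the footnote necessarily produces wrong percentages. The documents do not support that: they give no count of surgeons without a previous device, and with none the figures are identical. A share of all completed questionnaires, labelled as such, is also a correct answer to a different question. This stands, and it limits the point to what happens if someone answers *None* or leaves an item blank.
- **The form is not shown.** A reader might also infer that the rule flatters ENSEAL X1, or works against it. The questionnaire and its eCRF are not reproduced, so it is unknown whether *None* skips the comparative items. The direction is therefore unknown. This stands, but the full denominator suits neither case.
- **The table discloses part of it.** It prints the number of questionnaires, the *None* count and every category count, so in the blank case a careful reader could recover 6/9. That does not work when *None* surgeons answer; the reader would then need Listing 16. This mitigates the problem without removing it.
- **SAP 8.7 could be read as excluding blanks.** Perhaps, but the footnote says otherwise, and 8.7 does not deal with *None* surgeons who do answer.
- **N may exceed 12.** Protocol 3.3.1 lets sub-investigators use the device, and Protocol 3.4.3 asks every investigator for a questionnaire. A larger N shrinks the effect of each *None* answer, as the N = 24 row shows. The procedure columns remain smaller than the total.
- **The stakes are low.** The questionnaire is non-validated (Protocol 3.4.3), is listed under additional endpoints (SAP 8.4.3), and belongs to a study that tests no hypothesis. This is accepted.

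**Conclusion.** The point holds in conditional form. If at least one surgeon reports no previous advanced bipolar device, the footnote gives percentages for the four comparative items that do not describe surgeons able to compare. Blank answers understate every category; answers without a comparator can move agreement up or down. The gaps calculated above illustrate the mechanism and do not estimate its size in this study, because N, k and a are all assumed. Whether any distortion occurs, and in which direction, cannot be settled from the documents. The importance is minor. It is still worth correcting, because the rule is explicit, it differs from the SAP's own handling of conditional items, and it is easy to repair.

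**What to change.** Amend the Table 11 footnote. For the hand-fatigue, instrument-exchange, ease-of-use and critical-task items, set the denominator to questionnaires that report at least one previous advanced bipolar device and have a non-missing answer to that item. Print that n beside each item in every column. Keep all completed questionnaires as the denominator for the previous-device item and the cut/seal button item.

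The cost is one footnote, one filter in the table program and an n row per item; no new data are needed. SAP 8.1 treats added or reworded footnotes as minor modifications when the methodology is unchanged. A change of denominator may fall outside that, so it is safer to record it as a difference from the plan in the study report, as 8.1 provides.
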